In addition to this high-level social cognitive test, a low-level social cognitive test, the Affective Prosody Task (APT; [58]), will be used to measure auditory emotion recognition. Stimuli consist of audio recordings of semantically neutral sentences spoken with different voice tones. The sentences are either statements or questions and conveyed in 6 emotions (fear, anger, happiness, sadness, disgust, or neutral). After each stimulus, a list of the 6 possible choices is presented on the computer screen and the participant selects one emotion. It takes about 15 min to complete this task.

A social cognitive composite score will be created by standardizing (z-scoring) then summing the total scores from the MSCEIT Managing Emotions subtest and the APT. The social cognitive composite score will be included in exploratory analyses.

Functional Capacity and Community Functioning

To assess functional capacity, the UCSD Performance-based Skills Assessment (UPSA; [59]) will be administered. The UPSA assesses five skill areas that are considered essential to functioning in the community: General Organization; Finance; Social/Communications; Transportation; and Household Chores. The UPSA involves role-play tasks with props that are administered in the laboratory as simulations of events that the person may encounter in the community. These tasks are similar in complexity to situations that a community-dwelling person with chronic mental illness is likely to encounter. Inter-rater reliability of ratings are excellent (intraclass correlation coefficient = .91, $p < .001$). The UPSA takes 25 minutes to administer and yields a total score and domain scores. The UPSA total score will serve as the primary functional outcome measure.

To assess community functioning, the Role Functioning Scale (RFS; [60]) will be administered. The RFS assesses patients' current level of functioning in four areas: independent living skills, social (both family and non-family) functioning, and work functioning. The subscale ratings range from 1 (severely impaired) to 7 (maximal functioning) and include anchor points that detail both the quantity and quality of functioning. The RFS will be administered as part of an approximately 30-minute interview and rated by one of several trained interviewers in our lab. The RFS yields a total score and domain scores.

Although we are evaluating whether our relatively brief clinical trial affects proximal constructs such as cognition and functional capacity, we are unlikely to see significant changes in real-world functioning after only 3 months of cognitive training. Nonetheless, we will include the RFS total score in exploratory analyses, and these results might provide a basis for future work.

Half-way through the training, subjects will be administered two questionnaires, the Intrinsic Motivation Inventory for Schizophrenia Research (IMI-SR) and Theories of Intelligence Scale (TIS). The IMI-SR is a task-specific measure of intrinsic motivation. It consists of 21 items rated on a 7-point Likert scale with responses ranging from "not at all true" to "very true". It is designed to assess

patients' subjective experience of an activity in an experimental setting (i.e., cognitive training). The instrument has 3 subscales: 1) perceived interest and enjoyment due to task, 2) perceived value and usefulness of the task, and 3) perceived autonomy to perform the task. The TIS assesses subjects' beliefs about the nature of intelligence (as an unchangeable, fixed entity or as a malleable quality that can be developed). It consists of 8 items: 4 entity theory statements (e.g., "You have a certain amount of intelligence, and you really can't do much to change it") and 4 incremental theory statements (e.g., "You can always substantially change how intelligent you are").

Cognitive Training Interventions

Specific Perceptual Training: Brain Fitness Program, Posit Science, San Francisco, California
www.positscience.com

This computerized cognitive intervention is designed to improve the speed and accuracy of auditory information processing through increasingly more difficult stimulus recognition, discrimination, sequencing, and memory tasks under conditions of close attentional control, high reward, and novelty [61]. BFP consists of 6 exercises (Table 3). Stimuli across the exercises are chosen such that they span the acoustic and organizational structure of speech, from very simple acoustic stimuli and tasks (e.g., time order judgments of rapidly successive frequency-modulated sweeps) to complex manipulations of continuous speech (e.g., narrative memory). The exercises adaptively progress based on the subject's individual performance during a training session and become more challenging as the subject's abilities improve. Participants will work with 4 of the 6 exercises (for 15 min per exercise) in each session. Duration of training is 1 hour per day, 3 days per week, for 12 weeks, for a total of 36 hours.

Table 3: Brain Fitness Program Exercises

Exercise Name	Description
High or Low?	Reconstruct the identity (upward or downward) and sequence of frequency-modulated sweeps. The task progresses by changing the duration and interstimulus interval between the sweeps
Tell Us Apart	Identify a synthetically generated syllable (e.g., _ba_) from a confusable pair (e.g., _ba_ vs. _da_). The task progresses by changing the duration and intensity of the sweep component of the initial consonant.
Match It!	Match short spoken confusable consonant–vowel–consonant words (e.g., bad, dad) from a spatial grid. The task progresses by changing the number of potential matches and processing the spoken speech to stretch and emphasize rapid transitions.
Sound Replay	Reconstruct a sequence of short spoken words (identical to the third exercise stimuli). The task progresses by changing the number of words in the sequence and the level of speech processing.
Listen and Do	Reconstruct a spoken series of instructions by using the computer mouse to click and drag icons on the computer screen. The task progresses by changing the number and complexity of the instructions and the level of speech processing.
Story Teller	Answer questions regarding short narratives. The task progresses by changing the length of the narratives and the level of speech processing.

BFP has a strong theoretical rationale based on systems neuroscience principles. The goal of this neuroplasticity-based training program is to harness the brain's inherent plasticity through implicit

learning mechanisms. This training approach relies on the premise that the effects of implicit learning and repetitive practice are intact in schizophrenia despite the fact that explicit learning/memory and the motivation/reward systems are impaired [62]. The training employs intensive, repetitive, adaptive practice of well-defined skills to maximize enduring plastic changes in the brain. To drive learning and preserve reward schedules [63], the difficulty level for each subject is adjusted to maintain an approximately 85% correct rate and each correct trial is rewarded immediately with points and animations.

A large-scale RCT comparing BFP to a general cognitive stimulation program in healthy adults found greater improvements in auditory processing and better performance on untrained neurocognitive measures of attention and memory in the BFP group [64]. As mentioned above (Preliminary Studies), our laboratory has previously used Posit Science software with patients and found it to be very well tolerated.

Broad Cognitive Training: Cognitive Package (Cogpack; version 8.5, Marker Software, Ladenburg, Germany) www.cogpack.de

This computerized cognitive intervention is designed to provide training across a broad range of cognitive functions. Cogpack is well established in psychiatric hospitals and clinics in German-speaking countries [65] and has been translated into several languages, including English. Cogpack consists of domain-specific exercises, aimed at training specific cognitive areas (attention, working memory, verbal and visual memory, executive functioning, reasoning, language) and non-domain-specific exercises that require the use of several functions at a time. Although Cogpack includes low-level cognitive exercises (i.e., scanning, hand-eye coordination, and psychomotor speed), these exercises will not be included in this protocol to better separate bottom-up from top-down training interventions. Participants will complete a total of 48 exercises. All exercises are included within the first 9 sessions. Then, variants of the same exercises with different levels of difficulty are repeated over the remaining 27 sessions for further practice. In each session, the participant will work on a different subset of 4 to 6 exercises. Duration of training is 1 hour per day, 3 days per week, for 12 weeks, for a total of 36 hours.

Table 4: Cogpack Exercises

Domain Trained	Examples of Exercises
Attention	Sort out products on a conveyer belt, find the repeated character on a screen full of characters, press the bar when a number directly follows the previous one
Verbal and Visual Memory	Learn and memorize a list of words, remember addresses, images, labels, patterns, routes, details from lively scenes
Reasoning and Executive Functioning	Solve arithmetic problems and deductive comparisons, complete a block, continue a series, connect dots
Language	Use various clues to find words, answer questions about text-content, attribute quotations to authors or titles to poems, place syllables in order, solve anagrams
Knowledge and Everyday Skills	Demonstrate knowledge of facts, history, geography, country abbreviations, count bills, balance scale, use compass, estimate calories

Similar to the Brain Fitness Program, a motivational enhancement component is embedded in Cogpack to enhance intrinsic motivation and perceived competency, two client factors that influence responsiveness to treatment [66]. The exercises are designed to be enjoyable, reinforcing to

complete, and challenging, with difficulty gradually increasing over time. The level of difficulty is set based on the subject's performance during the course of the session. Moreover, the program provides regular individualized feedback on the subject's performance during the session and over the course of treatment.

Control Treatment: Commercial Computer Games (CCG).

This treatment condition is designed to control for the effects of computer exposure, contact with research personnel, time spent being cognitively active, and financial compensation for participation. A similar control condition of commercially available computer games has been used in previous cognitive remediation studies with schizophrenia [14]. This "placebo" condition also controls for the non-specific engagement of attentional systems through the reinforcement of graphics-based computer games and allows for responses to visual and motor stimuli and action events via computer-generated tasks. However, these games do not have the specific and systematic approach of highly focused, intensive, individualized neuroadaptive training of BFP, and they do not have the conceptual and higher-level training of Cogpack.

Participants in this condition will play highly enjoyable commercially available computer games for a total of 36 hours and will receive the same amount of contact with personnel and the same monetary and other reinforcements as participants in the experimental treatment groups. Subjects will participate in three 60-min sessions per week and will play 4 computer games, at 15 minutes per type of game, in each session. We will use 10 computerized games (e.g., visuospatial puzzle games, pinball-style games, target-aiming games). These games have been used by [name] group and selected according to the following criteria: 1) The game is subjectively challenging, reinforcing, and can hold subjects' interest and motivation for the required intervention period; 2) the game encourages the development of psychomotor skills (e.g. reaction time, hand-eye coordination); and 3) the game has no disturbing or highly emotional violent or sexual content as rated by the Entertainment Software Rating Board.

Data Management

Data management and statistical support will be provided by the VISN 22 MIRECC Data Core, directed by the co-investigator and statistical consultant, [name]. The data core is made up of multiple senior consulting faculty from the UCLA Departments of Biostatistics and Psychiatry as well as full-time staff statisticians, database and applications programmers, data managers and web designers. Its personnel have extensive experience supporting studies ranging from small pilot projects to large multisite centers and have a long history of collaboration on schizophrenia studies at the VA with Drs. [name], [name] and their research team. For this project, the data core will develop a customized VA intranet-based data system, including the subject registry, data dictionary, randomization system, data entry forms, project management tools and the centralized database which can accommodate both manual entry and electronic upload and merging of data from other sources. In particular, EEG data will be collected and processed on a separate computer, and the primary amplitude measures will be extracted and uploaded into the primary database. The system will be housed on the data core's secure VA servers and will feature numerous security and quality assurance features including double entry to verify data correctness, automatic logic and range checking, and strict protocols for data confidentiality, transfer and back-up including anonymized ID coding to protect subject privacy. All files are encrypted and the systems and tools are protected by 128-bit SSL, the secure socket layer technology used for sensitive transactions on the web. The system will be accessible only via the VA intranet and will employ a hierarchical system of password protected logins, allowing differential access to project team members as appropriate to their roles. Data will be accessed only through the system, not transported, and analyses will be performed on de-identified and aggregated data in consultation with the MIRECC Data Core.

Statistics and Power Analysis

Statistical Plan

The experimental design for this study is a 3-group randomized clinical trial, with assessments at baseline and the 12-week treatment endpoint. The aims correspond to comparisons of the effects of two active treatments to each other and to a control condition on neurocognition, EEG, and functional capacity. For each of these domains, we specify a primary outcome measure. For neurocognition we will use a composite score created by averaging the t-scores for the 6 neurocognitive domains of the MCCB. The main EEG measure will consist of the MMN amplitude at electrode Fz. For functional capacity we will use the total score from the UPSA. If significant treatment effects are found on any of the primary outcomes, we will perform secondary analyses on the corresponding components or subscale scores to determine whether the results are driven by particular aspects of the main constructs. To further characterize the treatment response profiles, exploratory analyses will be performed to examine the effects of the interventions on composite scores of social cognition and community functioning. We are well aware of the risk of Type I error inherent in a study with a large battery of assessments and have protected against it by clearly specifying a limited a priori set of primary outcome measures and contrasts of interest and designating all others as exploratory. However, since this is a preliminary study, designed to obtain estimates of treatment effects and to identify optimal intervention components and measures for a future definitive efficacy study, it is equally important not to miss any potentially relevant outcomes. All results will therefore be reported using an uncorrected two-sided significance level of $\alpha=.05$.

Prior to performing the primary analyses, descriptive statistics and graphical summaries will be obtained for all outcomes to check for missing data, outliers and the need for transformations or non-parametric methods. To assess the success of randomization, ANOVAs and chi-square tests will be used to test for baseline group differences on the primary outcomes as well as on demographic (age, gender, parental/personal education) and clinical (medication, duration of illness, and symptom severity) characteristics. Measures that show significant differences will be included as covariates in subsequent analyses. Below we give a detailed description of the analytic plan by specific aim.

Analysis Plan By Specific Aim:

Specific Aim #1: To compare the treatment effects of bottom-up training (BFP) to top-down training (Cogpack) as well as to a control condition on neurocognition.

Specific Aim #2: To compare the treatment effects of bottom-up training (BFP) to top-down training (Cogpack) as well as to a control condition on EEG (MMN).

Specific Aim #3: To compare the treatment effects of bottom-up training (BFP) to top-down training (Cogpack) as well as to a control condition on functional capacity.

Exploratory Aims: 1) To compare the treatment effects of bottom-up training (BFP) to top-down training (Cogpack) as well as to a control condition on social cognition and community functioning and 2) to assess whether changes in MMN are associated with changes in cognition and functioning.

Primary Analyses: To make the most efficient use of our data, our primary analytical technique will be the general linear mixed model (GLMM). GLMMs account for correlations induced by repeated measures within subjects, allow for both fixed and time-varying covariates and automatically handle missing data, producing unbiased parameter estimates provided that observations are missing at random. This allows us to include all available data from all subjects in the analyses, regardless of the degree of study participation or treatment dosage received, consistent with the intent to treat framework. For each of our primary outcomes (MCCB neurocognitive composite for Aim1, MMN amplitude at Fz for Aim 2, UPSA total score for Aim 3), our core model will include group (BFP, Cogpack, control) as the between subject factor, time (baseline, end of treatment) as the within subject factor, and a group by time interaction. Our primary hypotheses correspond to the group by time interactions comparing the outcome trajectories for the two active treatments, which can be obtained as post-hoc contrasts. Such contrasts can also be used to compare each of the active

treatments to the control condition, to test for within group change and to examine the magnitudes of group differences at the end of treatment.

Exploratory Analyses: Significant results for the primary global measures will be followed by equivalent models for the component subdomain scores to identify the primary drivers of treatment effects. Parallel models will also be fit for the exploratory analyses of social cognition and community functioning measures. To examine the relationships between MMN and cognition and functioning, we will add this EEG index as a time-varying covariate to the primary GLMM models for the other outcome domains. Although we are underpowered for a full mediation analysis, this will also allow us to obtain a preliminary indication of whether treatment effects operate through their effect on electrophysiology. Given that age, duration of illness, symptom severity, medication (indexed by CPZ units) and dosage of treatment (number of sessions) may all impact treatment response, we will also add these measures and their interactions with treatment group and time to the primary models to (i) determine whether they explain additional variation in the outcomes and (ii) obtain preliminary information about potential treatment moderators.

Attrition and Missing Data: We plan an intent-to-treat approach, using all available data from all subjects, regardless of the degree of program participation. As noted above, our GLMM models automatically handle missing data, making the most efficient use possible of available measurements. However, with this study population there is likely to be moderate data loss (up to 20% due to attrition and EEG artifacts based on our prior experience) and we recognize the potential for bias due to differential dropout. The impact of attrition will be evaluated by comparing dropout rates in the treatment arms using chi-square tests, and by comparing baseline characteristics of dropouts with those who have outcome data. If there is evidence that attrition patterns might introduce bias into the analyses, we will perform supplementary analyses adding propensity-score adjustments to the primary models. In the propensity score framework, baseline characteristics are used to develop a predictive model for attrition (e.g., via logistic regression), and the probability of dropout is used either as a covariate or to weight the observations in the subsequent models. In essence, cases who are similar to dropouts are weighted more heavily to “make up” for others like them who dropped out. As noted above, we will also explore treatment dosage as a covariate in secondary models. Finally, scattered missing data on covariates will be handled using multiple imputation procedures.

Power Considerations

We plan to enroll 120 subjects (n=48 for each of the two treatment conditions and n=24 for the control group) to obtain a final sample of n=96 subjects with complete data after accounting for attrition and data loss. Power calculations are conservatively based on these numbers and assume a two-sided significance level of $\alpha=.05$. We also assume a within-subject autocorrelation of $r = .7$, a value based on our experience with similar studies in the past. Our primary hypotheses all involve comparisons (parameterized as group by time interactions) among the 3 treatment groups. Our design provides over 80% power to detect overall effects as small as $f=.13$ which is sufficient to detect any pattern of changes in the three study arms for which the difference between the two most extreme groups is at least $d=.6$ at study endpoint. For the post-hoc comparison of primary interest, namely the group by time interaction examining the outcome trajectories for the two active treatment groups, this design provides sufficient power to detect an effect equivalent to a change from no difference at baseline to a difference of $d=.5$ at the post-treatment point. In addition, we note that we have over 80% power to detect within group changes from baseline to end of treatment of $d = .35$ in the active treatment groups and $d = .5$ in the control group, small to medium effects using the conventions of Cohen. For the exploratory analyses, the relationships will be assessed using the entire sample. This yields 80% power to detect a correlation of $r = .28$ between measures at any time point; power for the model with time-varying covariates will be higher due to the repeated measures.

In our pilot data, which examined performance on Cogpack training tasks in patients receiving two sessions per week over a 1 month period, we observed within group changes ranging from $d = .5$ (connect task) to $d = 2.5$ (confusion task). While these effect sizes cannot be used directly to compute power for our primary hypotheses (since they involve different measures and only a single group) they do show that patients can experience large cognitive changes over a much shorter period and with a lower intensity intervention than what is planned for this study. Since we are powered to detect small to medium effect-sizes magnitudes, we should be in a strong position even if effects are smaller on the global cognitive and functioning batteries.

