This proposal will determine which training approach leads to the largest magnitude of improvement in neurocognition, functional capacity, and neural functioning measured with EEG. Moreover, it will shed light on the underlying mechanism of action associated with the observed improvements in cognition. Based on the neuroscience-guided theoretical framework described above, we expect that the effects of the bottom-up training 1) will result in robust changes in higher-order cognitive operations, 2) will be evident at the earliest stages of auditory processing (normalization of MMN), and 3) will generalize to functional capacity. We also expect that the bottom-up training will lead to superior effects on the primary and secondary outcomes relative to the top-down training. The proposed study will help to decide how best to implement CR interventions to improve the cognitive and social functioning of patients with schizophrenia. Subsequent studies could consider additional research questions, such as whether the benefits of training are maintained over time. Depending on the results of this study, treatment providers at the VAGLAHS will be able to decide which version of CR will lead to more substantial gains. Our prediction is that it will be the neuroplasticity-based intervention. However, this study will provide a clinically meaningful answer, even if our hypothesis is incorrect.

Preliminary Studies

Previous Work on Neurocognition in Schizophrenia

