Subject recruitment will be coordinated through [name] ongoing studies. The availability of recruitment infrastructure, trained clinical interviewers, and cognitive remediation software will greatly facilitate the launch and conduct of the project. All subjects interested in the study will be prescreened for general inclusion and exclusion criteria by the recruiter using HIPAA compliant procedures. During the first visit (approximately 2 hours), participants will be consented and receive standardized clinical interviews to ensure diagnosis and eligibility. Participants will also receive symptom ratings of general psychiatric and negative symptoms, as well as mood symptoms. Subjects who fit selection criteria for the study will be scheduled for another visit, within 1 week of their first visit. During the second visit, (approximately 3.5 hours), subjects will be administered a comprehensive battery of cognitive, electrophysiological, and functional capacity/community functioning measures. Subjects will then be randomly assigned to one of the two cognitive remediation treatments (BFP and Cogpack) or to the control treatment (see randomization and treatment procedure below). Subjects will participate in 3 treatment sessions a week (1 hour each) for 12 weeks. After 18 treatment sessions, subjects will come back for a midpoint assessment visit (1.5 hours) in which they will be administered the electrophysiological measures again and two brief questionnaires. Upon completion of treatment, subjects will be scheduled for a post-treatment visit within 2 weeks of the last treatment session. This visit will last approximately 3.5 hours and will include the same clinical, cognitive, electrophysiological, and functional capacity/community functioning assessments that were administered prior to treatment. A urine toxicology screen will be conducted as part of each assessment visit. In the rare instance when a subject tests positive on the urine toxicology screen, he/she will be rescheduled to come back on a different day to complete the assessments. Overall, the study will consist of 4 visits (11 hours total) and 36 treatment sessions (36 hours total). Subjects will be compensated \$15/hour for the interview and testing sessions (first 2 visits, mid- and post-training visits) and \$10/hour for the treatment sessions, a rate deemed acceptable by our IRB. Funding is requested for four years of data collection (see Table 1). The IRB application will be prepared prior to the grant being funded.

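### The exploratory mechanism analysis pairs MMN with outcomes from the same visit and leaves the midpoint EEG unused, so it can show association but not how treatment works

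*Combined protocol and SAP*

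**What the plan says.** **The promise.** Background and Significance states that "it will shed light on the underlying mechanism of action associated with the observed improvements in cognition".

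**The visits.** Research Design and Methods gives the cognitive, EEG and functional measures together at the second (pre-treatment) visit. For the point after 18 of the 36 sessions, the plan states: "subjects will come back for a midpoint assessment visit (1.5 hours) in which they will be administered the electrophysiological measures again and two brief questionnaires"; no cognitive or functional test is listed there. The post-treatment visit "will include the same clinical, cognitive, electrophysiological, and functional capacity/community functioning assessments that were administered prior to treatment".

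**The model.** The Statistical Plan describes a three-group trial "with assessments at baseline and the 12-week treatment endpoint". Under Primary Analyses the core mixed model has "time (baseline, end of treatment) as the within subject factor". The second exploratory aim is "to assess whether changes in MMN are associated with changes in cognition and functioning". Under Exploratory Analyses, MMN is added as a time-varying covariate to the primary models for the other domains. The plan says the study lacks power for a full mediation analysis, but still expects a "preliminary indication of whether treatment effects operate through their effect on electrophysiology".

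**The concern.** Each outcome in the two-time model is paired with MMN from the same visit. Anything that varies from visit to visit and touches both measures, such as alertness or fatigue, makes MMN predict the outcome. Adding MMN then shrinks the treatment effect even if MMN plays no causal part. That is the pattern the Exploratory Analyses paragraph would take as a first sign that treatment operates through electrophysiology. The model cannot separate the two explanations, and a caveat about power covers imprecision, not bias.

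The midpoint EEG falls after randomisation and before the endpoint outcome visit. No outcome is measured at that visit, so the two-level model has nothing to pair with it, and no lagged model is described.

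At stake is the mechanism conclusion: independent effects of training on MMN and on cognition could be reported as a hint that one runs through the other.

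**Working it through.** **1. The plan's own figure.** Power Considerations gives 80% power for a correlation of .28 in the whole sample. By Fisher z with n = 96: atanh(.28) × √93 = 0.2877 × 9.644 = 2.774, and Φ(2.774 − 1.96) = 0.792. This reproduces. It is power to detect an association, and an association caused by shared state would be detected equally well.

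**2. Inputs.**
- From the documents: 38 completers in each active arm (Randomization and Treatment Procedure); within-subject correlation r = .7, d = .5 for the active-arm contrast and two-sided α = .05 (Power Considerations).
- Assumed: unit variances, so visit-specific error variance is 1 − .7 = .3; MMN scored so that higher is better; training effects of 0.5 SD on MMN and on the outcome at endpoint, with no effect of MMN on the outcome; same-visit error correlation ρ of .1, .2 or .3.

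**3. Same-visit model.** The within-person part of the planned model is the regression of outcome change on group and MMN change. Each change has variance 2 × .3 = .6, and their covariance is 2 × .3 × ρ. The slope is therefore .6ρ/.6 = ρ. The effect absorbed is ρ × 0.5, which is a share ρ of the 0.5 SD effect: **10%, 20%, 30%**. Separating between-person from within-person MMN does not help, because the artefact lies in the within-person part.

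The chance that the MMN coefficient is significant, with n = 76 and one group term, follows from δ = atanh(ρ) × √(76 − 1 − 3) = atanh(ρ) × 8.485:

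| ρ | δ | Significant (formula) | Significant (simulation, 4,000 trials) |
|---|---|---|---|
| .1 | 0.851 | 13.6% | 14% |
| .2 | 1.720 | 40.5% | 41% |
| .3 | 2.626 | 74.7% | 75% |

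With all three arms (38/38/19, n = 95, two group terms), the multiplier is √90 = 9.487 and the rates are 16%, 49% and 84%; a separate simulation of 3,000 trials per setting gave the same. At ρ = 0 the rate is about 5% to 6%.

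These are rates for the MMN coefficient alone. If a significant group effect on MMN is also required, the simulated rates are 10%, 33% and 59%. That agrees with multiplying by the power of the active-arm contrast, Φ(0.5/√(1.2/38) − 1.96) = 0.803, which gives 11%, 33% and 60%.

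**4. Midpoint model.** Regress the endpoint outcome on group, its own baseline, baseline MMN and midpoint MMN. Assume also a correlation of .2 between the stable parts of MMN and outcome. Cross-covariances are then .7 × .2 = .14 between visits and .14 + .3ρ within a visit. Solving the normal equations gives midpoint-MMN slopes of .054, .082 and .112.

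| ρ | Absorbed, midpoint effect .25 SD (slope × .25/.5) | Absorbed, midpoint effect .5 SD | Coefficient significant (simulation) |
|---|---|---|---|
| .1 | 3% | 5% | 8% |
| .2 | 4% | 8% | 11% |
| .3 | 6% | 11% | 16% |

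The like-for-like comparison with 10%, 20% and 30% is the .5 SD column. The rest of the reduction comes from assuming a smaller midpoint effect. The artefact is not zero, because baseline MMN and baseline outcome share a visit and the stable parts are correlated.

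**5. Power of the midpoint path.** With a .25 SD midpoint effect, the group difference in midpoint MMN has standard error √((2/38)(1 − .49)) = 0.164 and power Φ(0.25/0.164 − 1.96) ≈ 33%. Both legs must be significant, so this caps detection of the path. Simulations of complete true mediation, with varied assumptions on how much of the MMN response shows by midpoint, found both legs significant in about 4% to 17% of trials.

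**The case against.** **The plan is already cautious.** The analysis is labelled exploratory, full mediation is disclaimed, the aim speaks of association, and the Statistical Plan calls the study preliminary. A reader might infer that the plan commits to declaring mediation, or that 14% to 75% are rates of false mediation claims. The documents support neither: they promise only a preliminary indication, and those rates concern one coefficient. What remains is that the stated caveat is about power, while the sentence keeps a mechanistic reading.

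**Several state effects are controlled.** Urine toxicology is done at each assessment visit and positive subjects are rescheduled. Recent substance dependence or abuse is excluded, medication must be unchanged for six weeks before entry, and CPZ dose is a planned covariate. The Background describes MMN as preattentive. These points make large error correlations less obvious. They do not exclude shared alertness or fatigue, and the documents give no value either way.

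**Baseline MMN also precedes the outcome.** This is correct, so it would be wrong to call the midpoint EEG the only earlier MMN. It is the only such measurement after randomisation; baseline MMN cannot carry a treatment effect.

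**The lagged model is weak.** This stands. Its power is low, confounding of MMN and outcome remains, and without cognition at midpoint reverse order is not excluded. It cannot be the sole test of mechanism.

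**The working simplifies the plan.** It uses change-score and baseline-adjusted regressions, not the planned mixed model. It shows direction and range, not a forecast.

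**Conclusion.** The point holds as a minor one. The exploratory model is concurrent, its mechanistic reading is qualified only by power, and no stated analysis uses the midpoint MMN. With no true mediation, same-visit MMN absorbs about 10% to 30% of a 0.5 SD effect and is significant in about 14% to 75% of trials, for assumed error correlations of .1 to .3. At zero correlation there is no artefact. Midpoint MMN reduces the absorbed share to about 5% to 11% at equal effect size, or 3% to 6% if the midpoint effect is half as large.

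A reader might infer that the trial's main conclusions are affected. They are not: the group-by-time comparisons on MCCB, MMN and UPSA do not involve this covariate, and the randomised comparison of MMN under Aim 2 still bears on whether training changes it.

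**What to change.** In the Exploratory Analyses paragraph:

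1. Describe the same-visit MMN covariate model as a measure of association only, and remove the statement that it indicates how treatment effects operate.
2. Add a supportive exploratory lagged model: endpoint MCCB composite (and, separately, UPSA total) on group, its own baseline, baseline MMN and midpoint MMN. Report the indirect effect of group through midpoint MMN with an interval, for example by bootstrap.
3. State its limits beside it: MMN change after 18 sessions may be small and power is low, so a null result is not evidence against the mechanism; confounding and reverse order are reduced, not removed.

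List the midpoint EEG among the assessments in the Statistical Plan, and word the mechanism sentence in Background and Significance to match.

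The cost is wording and one extra exploratory model. The midpoint EEG is already scheduled, so no visit, subject or primary analysis changes. The main downside is an imprecise result that could be over-read if item 3 is left out.
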